5.3. Medical History

Medical history will be collected at screening for disease-specific and general conditions (ie, conditions not specific to the disease being studied).

HCT-specific medical history (eg, transplant type, graft versus host disease [GVHD], cell source, cytomegalovirus [CMV] status, and time from transplant to the first dosing date) will be summarized by treatment group and overall using descriptive statistics (n, mean, SD, median, Q1, Q3, minimum, and maximum) for continuous variables and using the numbers and percentages of subjects for categorical variables. A summary of HCT-specific medical history will be provided for the Safety Analysis Set. No formal statistical testing is planned.

General medical history will not be coded, but will be listed only.

6. EFFICACY ANALYSES

6.1. Primary Efficacy Endpoint

6.1.1. Definition of the Primary Efficacy Endpoint

The primary efficacy endpoint for this study is the time-weighted average change in \log_{10} RSV viral load from Baseline (Day 1) to Day 9, defined as:

$$\frac{\sum_{i=a}^{b-1} \{0.5 \times (Y_i + Y_{i+1}) \times (t_{i+1} - t_i)\}}{(t_b - t_a)}$$

where Y_i is the change from Baseline in RSV \log_{10} viral load at Visit i , t is the time at the specified timepoint (the actual study day), a is the baseline assessment at Day 1, and b is the last assessment at or prior to Day 9.

The time-weighted average change, often referred to as the DAVG, provides the average viral burden change from baseline.

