3.1.3. Per Protocol Analysis Set

The Per-Protocol (PP) Analysis Set includes subjects in the FAS who meet the following criteria:

- Did not violate the following major inclusion criteria (IC)
 - IC #2: Received an autologous or allogeneic HCT using any conditioning regimen
 - IC #3: Chest X-ray obtained < 48 hours prior to Screening
 - IC #4: Documented RSV in both the upper and lower respiratory tract as determined by local testing collected \leq 6 days prior to Day 1

- Did not administered invalid (eg, expired, damaged, quarantined, improperly stored) study drug
- Not be dispensed incorrect study drug (wrong bottle) or drug from another study
- Missed < 1 dose (200 mg) in the first 9 study days
- Missed < 3 nasal swab samples over the course of the study

The PP Analysis Set is the secondary analysis set for efficacy analyses.

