6.1.2. Analysis for the Primary Efficacy Endpoint

The primary analysis will test for the superiority of the presatovir group compared to the placebo group based on the time-weighted average change in \log_{10} RSV viral load from Day 1 to Day 9 in the Full Analysis Set at the 2-sided 0.05 level. The null and alternative hypotheses for the superiority test on the primary efficacy endpoint are as follows:

- H_0 : There is no difference between presatovir and placebo in the time-weighted average change in RSV \log_{10} viral load from Day 1 to Day 9
- H_1 : There is difference between presatovir and placebo in the time-weighted average change in RSV \log_{10} viral load from Day 1 to Day 9

To test the null hypothesis above, a parametric analysis of covariance (ANCOVA) model with corresponding baseline viral load and stratification factors (supplemental O₂ use and treatment of current RSV infection) as covariates will be used, at a 2-sided 0.05 level. Adjusted means and 95% confidence intervals (CIs) will be provided. The stratified Wilcoxon rank sum test will be implemented as a sensitivity analysis.

Viral load values below the limit of detection (LOD) will be assigned as 0 if it is reported in the form of ‘not detected’. A value of 1 unit less than the LOQ will be used for analysis if the viral load is reported in the form of “ $< x$ ” (where x is considered the LOQ). Viral load data will be transformed using the base 10 logarithm for the analyses and summaries. To account for 0 values, 1 will be added to each viral load measurement before being transformed.

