6.1.3. Sensitivity Analysis for Primary Efficacy Endpoint

Sensitivity analyses of the primary efficacy endpoint will be performed in the PP analysis set.

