6.1.4. Imputation of Missing Data

Missing viral load data due to premature discontinuation of the study will not be imputed as all available data will be included in the time-weighted average calculations. Intermediate missing viral load data will be imputed using the trapezoidal rule for the time-weighted average calculations.

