	Visit 1: Screening (Day -2 to -1)	Visit 2: Baseline Assessments, Randomization, and Treatment Assessments (Day 1)	Visit 3: Day 3 ^p (±24 hours)	Visit 4: Day 5 (±24 hours)	Visit 5: Day 7 (±24 hours)	Visit 6: Day 9 (±24 hours)	Visit 7: Day 13 (±24 hours)	Visit 8: Day 17 (±24 hours)	Visit 9: Day 22 (±24 hours)	Visit 10: End of study/Day 28 (+3 days)		Optional Extended Viral Monitoring ^k			
												Visit 11: Day 35 (±48 hours)	Visit 12: Day 42 (±48 hours)	Visit 13: Day 49 (±48 hours)	Visit 14: Day 56 (±48 hours)
Concomitant Medications	X	X	X ^m	X	X ^m	X	X	X	X	X					

- a Chest X-ray obtained < 48 hours prior to Screening may be used
- b Existing values collected \leq 6 days prior to Screening may be used
- c Required for women unable to confirm menopause, hysterectomy and/or bilateral oophorectomy
- d On room air
- e Central laboratory testing: hematology and serum chemistry to include WBC with differential, Hgb, platelets, BUN, creatinine, serum albumin, AST, ALT, ALP, and total bilirubin
- f 2 samples total, 1 from each nostril – collected prior to dosing on dosing days
- g PK samples collected for all subjects 4 hours (\pm 30 mins) post-dose Day 1; pre-dose on Days 5, 9, 13, and 17; and anytime on Day 22
- h For hospitalized subjects only: blood will be drawn for serum creatinine at 4 hours (\pm 30 mins) post-dose at Visit 2 (Day 1) and at any time on Days 2, 3 and 4 (approximately 24, 48 and 72 hours post-first presatovir dose if they remain hospitalized at those times).
- i For hospitalized subjects only: PK sample collected at Visit 3 (48 hours [\pm 3 hours] post-first presatovir dose)
- j Only for subjects who agree to the Optional Extended Viral Monitoring at the time of consent
- k Only for subjects who agree to the Optional Extended Viral Monitoring at the time of consent and test positive (or inconclusive) for RSV at Visit 9 (Day 22)
- l Assessment of procedure-related AEs only, if home visit.
- m Not required if home visit.
- n Local troponin testing will be done pre-dose in accordance with the standard assay available and used at the site. Point-of-care “rapid” troponin tests are not acceptable for protocol-mandated troponin testing.
- o If only the upper or lower respiratory tract was assessed prior to consent, a separate local RSV test in the tract not previously assessed must be performed. Subjects who were not tested for RSV as standard of care may consent to the study and be tested for RSV during the Screening visit.

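### Does ending the primary Day 1 to Day 9 viral-load average at each subject's own last swab leave the primary analysis in need of correction?

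*SAP*

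**What the plan says.** Section 6.1.1 defines the endpoint as the trapezoidal area under the change from baseline in log10 viral load, divided by the time from the first to the last assessment used. The limits are given as "a is the baseline assessment at Day 1, and b is the last assessment at or prior to Day 9". The change is indexed by visit, and the time scale is described by "t is the time at the specified timepoint (the actual study day", with the bracket closing there.

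Section 6.1.4 covers missing data: "Missing viral load data due to premature discontinuation of the study will not be imputed as all available data will be included". Gaps between observed swabs are bridged by the trapezoidal rule.

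Two checks on the primary analysis are named. Section 6.1.2 says "The stratified Wilcoxon rank sum test will be implemented as a sensitivity analysis", and Section 6.1.3 says "Sensitivity analyses of the primary efficacy endpoint will be performed in the PP analysis set". Among the per-protocol conditions in Section 3.1.3 are "Missed < 1 dose (200 mg) in the first 9 study days" and "Missed < 3 nasal swab samples over the course of the study".

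Appendix 1 schedules Visit 6 at Day 9 with a tolerance of 24 hours either way. Section 1.2 also labels Visit 6 as Day 9. Appendix 3 drafts a repeated-measures model for viral load, and Section 12.1 lists a further time-weighted average table (15.9.3.2). The text governing the exploratory analyses, Section 6.3.2, is blacked out.

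**The concern.** The hypothesis in Section 6.1.2 concerns Day 1 to Day 9, but the denominator is each subject's own observed span. If viral load is still falling, a shorter span gives a smaller average change, so early stopping pulls a subject's score towards zero. Similar stopping in both arms dilutes the treatment difference. Unequal stopping can create a difference where none exists, or hide a real one.

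Neither named check addresses this. The Wilcoxon test is given no other derivation of the endpoint. The per-protocol repeat probably removes most permanent early stoppers, because they miss the Day 9 dose or three or more swabs, but it does so on post-randomization grounds and leaves the derivation unchanged. It also keeps a subject who is dosed at Visit 6 and lacks only that swab. That counts as one missed visit or, since Appendix 1 specifies "2 samples total, 1 from each nostril", as two missed samples; both are below the limit of three.

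The second worry is the boundary. Study day is a calendar calculation (Section 3.8.1), so a compliant Visit 6 swab can fall on Day 10. If Day 9 in the definition means the actual day, that swab is lost and the span ends at Day 7. If it means the nominal visit, the swab is kept. Two programmers could then derive different primary values for the same subject.

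**Working it through.** **Plan's own figure (Section 1.3).** Inputs: difference 1.5, SD 1.75, 25 per group, 2-sided 0.05. Standard error = 1.75 × √(2/25) = 0.495. Power is 85.8% by the normal approximation and 84.4% by the noncentral t with 48 df; the plan says about 85%. Randomized total: 50/0.85 = 58.8, so 59; the plan says 60. With 30 per arm and nobody truncated, power is 90.4%.

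**Assumed decline shapes.** The SAP gives none. I used a linear fall and plateau curves 1 − 2^(−(t−1)/h) with half-life h of 6, 4, 2 and 1 days, applying the trapezoid to Days 1, 3, 5, 7 and 9. Each entry is the subject's score relative to the full Day 1 to Day 9 value.

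| Curve | Last swab Day 5 | Last swab Day 7 | Visit 6 swab on Day 10, kept |
|---|---|---|---|
| Linear | 0.500 | 0.750 | 1.125 |
| h = 6 | 0.568 | 0.800 | 1.088 |
| h = 4 | 0.598 | 0.820 | 1.075 |
| h = 2 | 0.675 | 0.867 | 1.049 |
| h = 1 | 0.769 | 0.917 | 1.028 |

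If viral load fell to Day 5 and returned fully to baseline by Day 9, the Day 5 ratio would be 1.00.

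**Equal stopping, 20% of each arm at Day 5.** Difference = 1.5 × (0.80 + 0.20 × ratio).
- Linear: 1.5 × 0.900 = 1.350. At h = 1: 1.5 × 0.954 = 1.431.
- Power at 25 per arm: 76.2 to 80.8%.
- Power at 30 per arm: 83.6 to 87.6%.

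Truncated subjects stay in the Full Analysis Set, which asks only for a full dose and a quantifiable Day 1 swab (Section 3.1.2). The 25-per-arm figure therefore combines a loss of five per arm with a further 20% truncated.

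**Unequal stopping, no true effect.** With a common full-window change of −1.5 and 20% against 5% stopping at Day 5, the spurious difference is 1.5 × (1 − ratio) × 0.15.
- Linear: 1.5 × 0.500 × 0.15 = 0.11. At h = 1: 1.5 × 0.231 × 0.15 = 0.05.
- Against a standard error of 0.495, type I error is 5.1 to 5.6%.
- Harsher case: 30% stopping in placebo and none in presatovir, linear decline, gives 1.5 × 0.5 × 0.30 = 0.225 and about 7.4% (normal approximation).

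**One-sided stopping with the planned effect** (linear, 25 per arm, normal approximation). With 15% stopping at Day 5 in presatovir only, the presatovir mean is −3.0 × (0.85 + 0.15 × 0.5) = −2.775, the difference is 1.275 and power is 73%. The mirror case in placebo gives 1.61 and 90%.

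**Day 10 wording, 20% attending on Day 10.**
- Dropped: 1.5 × (0.80 + 0.20 × 0.75) = 1.425 (linear) to 1.475 (h = 1); power at 25 per arm 80.5 to 83.1%.
- Kept: 1.5 × (0.80 + 0.20 × 1.125) = 1.538 (linear) to 1.508 (h = 1); power 86.1 to 84.8%.
- The literal reading costs at most 1.5 × 0.20 × 0.25 = 0.075 log10 against the full-window value. The two readings differ by at most 0.11.

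**The candidate remedy.** A full-window contrast from the Appendix 3 model would weight the visit estimates for Days 3, 5, 7 and 9 by 2/8, 2/8, 2/8 and 1/8. Visit 3 is optional for subjects not in hospital (Appendix 1), so a version without Day 3 uses 3/8, 2/8 and 1/8. It recovers 0.985 of the full average at h = 6, 0.952 at h = 2 and 0.911 at h = 1. At h = 1 it turns 1.5 into 1.37, further from the target than the 1.43 left by the truncation it is meant to check. At h = 2 the two are close (1.43 and 1.40).

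**The case for a change.** The strongest case for acting is that both edits are cheap and could be made while blinded: one phrase fixing the end of the window, and one contrast in a model already drafted. Disposition tables, by-visit summaries and listings would reveal uneven stopping but would not re-estimate the effect, and the per-protocol set is no substitute. All of that stands as description. In a small trial, strongly lopsided stopping would matter, as the harsher cases above show.

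It falls short of a correction for three reasons.
- The contrast assumes data are missing at random and implicitly projects viral load past death, which the present rule does not do. Its nominal-day weights differ from the primary's actual-day weights, so a gap between the two results would not isolate truncation.
- The absence of a full-window analysis cannot be established. Section 6.3.2 is blacked out, and the derivation behind Table 15.9.3.2 cannot be read. Nothing should be claimed either way about what they contain.
- The Day 10 reading passes over the SAP's own indexing. The visit identifies the measurement and the actual day supplies its time weight. The nominal-visit rule in Section 3.8.2 is written for by-visit summaries, so it supports this reading without settling it.

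**Conclusion.** No change follows. Averaging to the last available swab is an openly stated and reproducible trade-off, and Sections 6.1.1 and 6.1.4 agree on it. On the assumed curves, 20% stopping at Day 5 in both arms would trim the 1.5 log10 difference by 0.07 to 0.15. With 30 per arm, power stays at about the planned level or above. A 15-point imbalance in stopping barely moves the type I error. Larger or one-sided stopping would matter more, but the SAP gives no rates that make it likely, and the planned disposition and by-visit outputs would expose it.

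The Day 9 boundary is a small gap in wording that analysts would fill sensibly by taking nominal Visit 6, with the actual day used only for the time weight. A full-window model contrast is a reasonable optional extra with drawbacks of its own, not a repair. All sizes rest on assumed decline shapes, stopping rates and Day 10 attendance, with the SD held at 1.75.

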6.1.2. Analysis for the Primary Efficacy Endpoint

The primary analysis will test for the superiority of the presatovir group compared to the placebo group based on the time-weighted average change in \log_{10} RSV viral load from Day 1 to Day 9 in the Full Analysis Set at the 2-sided 0.05 level. The null and alternative hypotheses for the superiority test on the primary efficacy endpoint are as follows:

- H_0 : There is no difference between presatovir and placebo in the time-weighted average change in RSV \log_{10} viral load from Day 1 to Day 9
- H_1 : There is difference between presatovir and placebo in the time-weighted average change in RSV \log_{10} viral load from Day 1 to Day 9

To test the null hypothesis above, a parametric analysis of covariance (ANCOVA) model with corresponding baseline viral load and stratification factors (supplemental O₂ use and treatment of current RSV infection) as covariates will be used, at a 2-sided 0.05 level. Adjusted means and 95% confidence intervals (CIs) will be provided. The stratified Wilcoxon rank sum test will be implemented as a sensitivity analysis.

Viral load values below the limit of detection (LOD) will be assigned as 0 if it is reported in the form of ‘not detected’. A value of 1 unit less than the LOQ will be used for analysis if the viral load is reported in the form of “ $< x$ ” (where x is considered the LOQ). Viral load data will be transformed using the base 10 logarithm for the analyses and summaries. To account for 0 values, 1 will be added to each viral load measurement before being transformed.

6.1.3. Sensitivity Analysis for Primary Efficacy Endpoint

Sensitivity analyses of the primary efficacy endpoint will be performed in the PP analysis set.

6.1.4. Imputation of Missing Data

Missing viral load data due to premature discontinuation of the study will not be imputed as all available data will be included in the time-weighted average calculations. Intermediate missing viral load data will be imputed using the trapezoidal rule for the time-weighted average calculations.

6.2. Secondary Efficacy Endpoints

6.2.1. Definition of Secondary Efficacy Endpoints

Secondary efficacy endpoints include:

- Number of supplemental O₂ free days through Day 28
- Proportion of subjects developing respiratory failure (of any cause) requiring mechanical ventilation (invasive or noninvasive) through Day 28
- Proportion of all-cause mortality among subjects through Day 28

6.2.2. Analysis Methods for Secondary Efficacy Endpoints

In order to account for multiple hypothesis testing of endpoints, a sequential testing procedure described in Section 3.5 will be used to control the overall Type 1 error rate of 0.05 across the primary and secondary endpoints.

The FAS will be used for all summaries and analyses of secondary endpoints. All secondary endpoints will be analyzed using 2-sided tests to compare treatment differences.

The number of supplemental O₂-free days through Day 28 will be analyzed using a negative binomial model with stratification factors as covariates and an offset parameter to account for the on-study duration. Subjects who die prior to Day 28 (inclusive) or are receiving supplemental O₂ on all days of the study period are assigned 0 supplemental O₂-free days. All survivors accrue 1 supplemental O₂-free day for each day that they are both alive and on the use of supplemental O₂ less than 12 hours per 24 hours (0:00 to 23:59) when they are on study.

The proportion of subjects who develop respiratory failure requiring mechanical ventilation and the proportion of subjects with all-cause mortality will be analyzed using Cochran-Mantel-Haenszel (CMH) test adjusting for the stratification factors at the 2-sided 0.05-level. The 2-sided 95% exact CI of the respiratory failure rate or mortality rate based on the Clopper-Pearson method will be provided for each treatment group. In the case of a small number of events, the exact method will be used.

[figure not shown]

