6.4. Changes From Protocol-Specified Efficacy Analyses

- The number of supplemental O₂-free days through Day 28 will be analyzed using a negative binomial model with stratification factors as covariates. An offset parameter will be included to account for differential study durations.

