13. APPENDICES

Appendix 1. Study Procedures Table

	Visit 1: Screening (Day -2 to -1)	Visit 2: Baseline Assessments, Randomization, and Treatment Assessments (Day 1)	Visit 3: Day 3 ^p (±24 hours)	Visit 4: Day 5 (±24 hours)	Visit 5: Day 7 (±24 hours)	Visit 6: Day 9 (±24 hours)	Visit 7: Day 13 (±24 hours)	Visit 8: Day 17 (±24 hours)	Visit 9: Day 22 (±24 hours)	Visit 10: End of study/Day 28 (+3 days)	Optional Extended Viral Monitoring ^k			
											Visit 11: Day 35 (±48 hours)	Visit 12: Day 42 (±48 hours)	Visit 13: Day 49 (±48 hours)	Visit 14: Day 56 (±48 hours)
Must complete visit in the hospital or clinic	X	X		X		X	X	X	X	X				
Written Informed Consent	X													
Medical History and Demographics	X													
Chest X-ray	X ^a													
Screening Labs	X ^b													
Urine or Serum Pregnancy Test ^c	X	X		X		X	X	X						
Vital Signs (inc. O ₂ Saturation ^d)	X	X	X ^m	X	X ^m	X	X	X	X	X				
Height	X													
Weight	X	X		X		X	X	X	X	X				
12-lead ECG		X						X		X				

	Visit 1: Screening (Day -2 to -1)	Visit 2: Baseline Assessments, Randomization, and Treatment Assessments (Day 1)	Visit 3: Day 3 ^b (±24 hours)	Visit 4: Day 5 (±24 hours)	Visit 5: Day 7 (±24 hours)	Visit 6: Day 9 (±24 hours)	Visit 7: Day 13 (±24 hours)	Visit 8: Day 17 (±24 hours)	Visit 9: Day 22 (±24 hours)	Visit 10: End of study/Day 28 (+3 days)	Optional Extended Viral Monitoring ^k	Visit 11: Day 35 (±48 hours)	Visit 12: Day 42 (±48 hours)	Visit 13: Day 49 (±48 hours)	Visit 14: Day 56 (±48 hours)
											Visit 11: Day 35 (±48 hours)	Visit 12: Day 42 (±48 hours)	Visit 13: Day 49 (±48 hours)	Visit 14: Day 56 (±48 hours)	
Local Troponin Test ⁿ		X							X		X				
Safety Labs ^e		X		X		X	X	X	X	X					
RSV antibody titer		X									X				
RSV Viremia		X		X		X	X	X	X	X					
Nasal Samples ^f	X ^o	X	X	X	X	X	X	X	X	X	X	X	X	X	X
Local RSV Testing	X ^o									X ^j					
Randomization		X													
IMP Administration		X		X		X	X	X							
PK Sample		X ^g	X ⁱ	X ^g		X ^g	X ^g	X ^g	X ^g						
Serum creatinine		X ^h	X ^h												
Adverse Events	X	X	X ^l	X	X ^l	X	X	X	X	X	X ^l	X ^l	X ^l	X ^l	
Review ICU admissions, hospitalizations, standard of care test results, mechanical ventilation, and supplemental O ₂		X	X ^m	X	X ^m	X	X	X	X	X					

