Appendix 4. Sample SAS Code for Negative Binomial Model

The following model statement may be used for the analyses of number of hospital-free day, ICU-free day, and ventilator-free day described in Section 6.3.2:

```
proc genmod data=dataset;
  class trt strata;
  model count = trt strata / offset=logt dist=NB;
run;
```

where logt is the offset parameter defined as the natural logarithm of study duration for each subject to account for potential differential study durations due to early discontinuations.

In the event that the negative binomial model fails to converge, a zero-inflated negative binomial model may be fit (dist=ZINB).

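### The offset in the O2-free-days model shortens exposure for deaths already scored 0 through Day 28, so an earlier death counts less

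*SAP*

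**What the plan says.** Section 6.2.2 sets the scoring rule and the model for supplemental-O2-free days in one paragraph.

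- **Deaths:** "Subjects who die prior to Day 28 (inclusive) or are receiving supplemental O₂ on all days of the study period are assigned 0 supplemental O₂-free" (the unit is days). The day of death plays no part.
- **Survivors:** "All survivors accrue 1 supplemental O₂-free day for each day that they are both alive and on the use of supplemental O₂ less than 12" (the limit is in hours per day), while they are on study.
- **Model:** a "negative binomial model with stratification factors as covariates and an offset parameter to account for the on-study duration".

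Section 6.4 lists the model as a change from the protocol and repeats the offset: "An offset parameter will be included to account for differential study durations".

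Appendix 4 gives sample code for the hospital-, ICU- and ventilator-free-day counts, "where logt is the offset parameter defined as the natural logarithm of study duration for each subject", and states its purpose as "to account for potential differential study durations due to early discontinuations".

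None of these places says what duration a subject who dies receives, and none exempts deaths from the offset. Section 3.5 puts this endpoint first among the secondary endpoints, ahead of respiratory failure and all-cause mortality.

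**The concern.** An offset is correct when the count can accrue only over the time observed. That is the case for a survivor who leaves early: days after withdrawal are unknown, and the offset turns the count into a rate over known days. It is not the case for a death. The scoring rule has already decided that the whole 28-day window is worth 0, so no unobserved time remains to adjust for. Shortening the exposure as well changes 0 of 28 into 0 of d.

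The scoring rule treats all deaths through Day 28 as equally bad. The offset undoes this and makes an early death less adverse than a late one. The rate ratio then depends on when subjects die as well as on how many die and how the survivors fare.

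Two things are at stake: the estimate for the first secondary endpoint, and, through the fixed sequence, the test that decides whether respiratory failure and mortality are formally tested at all.

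**Working it through.** **Inputs.** The SAP states no power, death rate or death timing for this endpoint, so there is no planned figure to reproduce. The 25 per arm is the evaluable number in section 1.3. Everything else below is assumed.

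**Step 1: weight of one zero.** Under a negative binomial model with daily rate r, exposure t and dispersion k, the expected count is mu = r × t. A zero contributes ln(1 + k × mu)/k to the negative log-likelihood and pulls on the log rate with weight mu/(1 + k × mu). With assumed r = 0.6 and k = 1:

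| Exposure given to the death | mu | ln(1 + mu) | mu/(1 + mu) |
|---|---|---|---|
| 3 days | 1.8 | 1.03 | 0.643 |
| 14 days | 8.4 | 2.24 | 0.894 |
| 28 days | 16.8 | 2.88 | 0.944 |

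The zero weighs less the earlier the death. The last column levels off, so the loss is concentrated in deaths during the first days.

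**Step 2: 5 deaths versus 0, 25 per arm.** These are maximum-likelihood fits with treatment only (no strata).

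- Arm without deaths, assumed free days: 0, 0, 0, 0, 3, 5, 8, 10, 12, 14, 16, 18, 20, 22, 24, 25, 26, 27 and seven values of 28. The total is 426.
- Arm with deaths, 20 survivors: 0, 0, 0, 3, 5, 8, 10, 14, 16, 18, 20, 22, 25, 26 and six values of 28. The total is 335, plus five zeros.

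With 28 days for everyone, the rate ratio is (335/25)/(426/25) = 13.40/17.04 = 0.786. With the offset ending at death:

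| Day of the 5 deaths | Rate ratio |
|---|---|
| all Day 1 | 0.902 |
| all Day 2 | 0.866 |
| all Day 3 | 0.845 |
| all Day 5 | 0.823 |
| all Day 10 | 0.801 |
| all Day 14 | 0.794 |
| Days 4, 9, 14, 19, 25 | 0.800 |

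**Step 3: equal deaths, identical survivors.** With 5 deaths per arm (the 20-survivor list in both), Day 2 versus Day 27 gives 1.074 in favour of the earlier-death arm. With log(28) it is 1.000. Deaths staggered over Days 4–16 versus Days 12–27 give 1.01.

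A second data set had 30 per arm, with 24 identical survivors (408 free days) and 6 deaths in each arm. Day 3 versus Day 25 gives 1.066 instead of 1.000. The crude ratio of days to exposure is (408/690)/(408/822) = 1.19, where 690 = 24 × 28 + 6 × 3 and 822 = 24 × 28 + 6 × 25.

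**Step 4: can the direction reverse?** Take two identical arms of 25 and let the five lowest scorers in one (0, 0, 0, 0, 3) die on Day 2. The ratio is 1.115 instead of 0.993, so the arm with the deaths looks better. With the same deaths spread over the period it is 1.014.

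**Step 5: simulation.** Mortality was equal in both arms (10% to 30%), with 25 or 30 per arm and survivors drawn alike. Deaths fell on Days 2–7 in one arm and Days 15–28 in the other. The mean rate ratio was 1.04 to 1.08 with the offset ending at death and 1.00 to 1.01 with 28 days. When death times were alike in both arms it was 1.01 under either offset. The null rejection rate was at most 1.7% throughout.

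**Step 6: visit window.** Appendix 1 lets the end-of-study visit fall up to three days after Day 28, and duration is not capped, while the count stops at Day 28. Random durations of 28 to 31 days in two identical arms gave ratios of 0.98 to 1.02 (2.5th to 97.5th percentiles of 100 draws).

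**The case against.** The SAP never says that duration ends at death. The only explicit definition of the offset is in sample code for other free-day endpoints, and its stated purpose, early discontinuation, could lead a programmer to give deaths 28 days anyway. This is fair as to wording: one reading step is needed. But on-study duration ordinarily ends at death, Appendix 4 applies it to each subject, and nothing in 6.2.2 or 6.4 overrides that. If 28 days was intended, the sentence saying so is absent and the remedy is the same.

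The stronger objection is size. With deaths spread over the period, the 5-versus-0 ratio moves from 0.79 to 0.80. The 95% intervals are almost the same: 0.40 to 1.56 with 28 days and 0.42 to 1.52 with the SAP offset. Large shifts need deaths packed into the first days, and nothing in the SAP suggests that pattern. No contrast comes near significance (all p about 0.5 or more), and no inflation of type I error appeared. In the 5-versus-0 case the direction stays right even with every death on Day 1. All-cause mortality is its own secondary endpoint, so excess deaths would be seen. All of this stands and limits the weight of the point. It does not make the offset right for deaths. The window effect in Step 6 is minor.

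**Conclusion.** The concern holds. Read plainly, section 6.2.2 applies two rules to the same deaths that do not fit together: a score fixed at 0 for the full window, and an exposure cut at the day of death. The result is a distorted estimate and a wrong ordering of outcomes, not a demonstrated error in the significance level.

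In the illustrations the rate ratio moves by about 0.01 when deaths are spread out or occur mid-period, and by about 0.06 to 0.12 when they all fall on Days 1 to 3 in one arm. It is about 4% to 8% too high on average when equal numbers of deaths come in the first week in one arm and after two weeks in the other. There is no distortion when the number and timing of deaths match between arms. These sizes rest on assumed survivor scores, death counts and death days, and on fits without strata. The primary endpoint is unaffected. The point should be fixed, because it concerns the first secondary test and the correction is small.

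**What to change.** In sections 6.2.2 and 6.4, define the exposure in the offset:

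- 28 days, so log(28), for every subject who dies through Day 28 and every subject followed through Day 28;
- the actual time on study only for subjects who withdraw alive before Day 28;
- a cap of 28 days, so that a late end-of-study visit adds no exposure.

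Apply the same rule to the free-day endpoints in Appendix 4 only if they also score deaths as 0; their definitions are redacted in the public SAP.

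The cost is one sentence in the SAP and one line of derivation code, with no new data. It should be settled before the blind is broken, because choosing the exposure for deaths after seeing when they occurred would be data-driven.
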